7.3.2 Day 1 of each subsequent cycle

- Physical examination
- ECOG performance status
- Vital signs (including weight)
- Triplicate ECGs should be assessed before the patient takes the study drug that day, before other procedures, and after the patient has rested for at least 3 minutes. Each recording should be separated by at least 30 seconds.
- Hematology (including ALC, ANC, RBC, reticulocytes, hemoglobin, hematocrit, 5-part differential, platelet counts, and PT/PTT/INR)
- Biochemistry (sodium, potassium, phosphate, chloride, creatinine, total calcium, total CO₂ or venous HCO₃, albumin, total protein, AST, ALT, ALP, total bilirubin, direct bilirubin, LDH, glucose, CK [if CK is elevated and elevation is clinically significant in the judgment of the Investigator, then CK-MB, troponin I, and myoglobin should be reactively tested, with further follow-up as clinically warranted], urea nitrogen, and uric acid)
- Urinalysis
- Pharmacokinetics
 - A pre-dose PK sample will be collected on Cycle 2, 3, 4, and 6 Day 1 only (See Appendix F).
- Tumor biopsy (optional) (Cycle 2 only)
- Review patient diary

Patients will remain on treatment as long as, in the opinion of the Investigator, they are deriving benefit and the withdrawal criteria listed in Section 7.6 are not met. Please refer to the Schedule of Assessments for detailed outlines of each visit during the treatment period for each part of the study.

7.3.3 Biomarkers (circulating tumor [ctDNA] and circulating tumor cells [CTC]) - Assessments Every 2 Cycles

Patients will be evaluated with ctDNA assessments at the pre-dose visit, on Day 1 of Cycle 1 and Cycle 2, and at the EOT visit.

CTC assessments will be evaluated at pre-dose, on Day 1 of Cycle 1 and Cycle 2, and on Day 1 of all even numbered cycles thereafter. The CTC assessments should also be collected at the EOT visit.

CONFIDENTIAL

Study Drug: AC699 Sponsor/Development Innovations Study Numbers: AC699-001/BRE 401

7.3.4 Imaging Assessments

Patients will be evaluated for response after 2 cycles of treatment. Response will be assessed every 2 cycles / 8 weeks (± 5 days) for the first year of treatment, and then every 4 cycles / 16 weeks (± 5 days) thereafter.

The following assessments will be performed if abnormal at baseline or if clinically indicated:

- CT scan of chest/abdomen/pelvis to include adrenal glands (CT scan of abdomen and pelvis required if adrenal glands are not included on CT scan of chest). An MRI may be performed in place of a CT scan at the discretion of the Investigator. However, the same imaging modality should be used throughout the study to image a given lesion.
- CT scan head/MRI brain if history of central nervous system (CNS) metastasis
- Bone scan or CT/PET scan if history of bone metastases.

The assessments to be performed at this time are specified in Appendix B. Please refer to Section 9 for further instructions on evaluating response (e.g., PD, SD).

7.4 Follow-Up Periods and Study Completion

7.4.1 End-of-Treatment Visit

The EOT visit, including collection of ctDNA and CTCs, will be performed after study completion or permanent discontinuation of study treatment for any reason, as soon as possible (preferably within 7 days but no later than 14 days), or when the Investigator decides with the patient to permanently discontinue the study treatment, or when the Investigator becomes aware that the study treatment has been discontinued.

The assessments for the EOT visit will then be performed at the next planned visit.

7.4.2 Thirty-Day Safety Follow-up

All patients will be followed during the off-treatment period until all treatment-related toxicity resolves, or 30 days (\pm 5 days) post-study drug discontinuation, or until the start of another anticancer treatment. Any concomitant medications received up to 30 days after the last dose of study drug should be recorded.

7.4.3 Extended Follow-Up Period

Patients discontinuing study treatment for reasons other than radiographic disease progression will began an extended follow-up period to continue monitoring disease status (after the 30-day safety follow-up). The response assessments will be performed every 8 weeks (\pm 5 days) (from the patient's initial Cycle 1 Day 1 visit) for the first year and then every 16 weeks (\pm 5 days), thereafter. Patients will attend the extended follow-up visits until disease progression occurs based on RECIST Version 1.1 (see Appendix B) or another withdrawal criterion is met such as:

- Start of a new anti-cancer therapy
- Lost to follow-up
- Death
- Patient withdrawal
- End of the whole study.

CONFIDENTIAL

Study Drug: AC699 Sponsor/Development Innovations Study Numbers: AC699-001/BRE 401

7.5 Study Completion

The study duration includes recruitment period and 12 month follow-up of the last patient. Patients may remain on treatment in the absence of disease progression at the completion of the study through a single patient IND or an expansion protocol, depending on the number of patients.

The Sponsor has the right to close this study or part of the study at any time, which may be due but not limited to the following reasons:

- If risk-benefit ratio becomes unacceptable evident by emerging data.
- If the study conduct does not suggest a proper completion of the trial within a reasonable time frame.

The Investigator has the right to close his/her center at any time.

For any of the above closures, the following applies:

- Closures should occur only after consultation between involved parties. Final decision on the closure must be in writing.
- All affected institutions must be informed as applicable according to local law.
- All study materials (except documentation that must remained stored at the site) must be returned to the Sponsor. The Investigator will retain all other documents until notification is given by the Sponsor for destruction.
- In the event of a partial study closure, on-going patients, including those in post study follow-up, must be taken care of in an ethical manner.

Details for individual patient's withdrawal can be found in Section. 5.2.

7.6 Early Patient Termination/Patient Withdrawal

Patients who discontinue treatment early due to disease progression, a DLT, or withdrawal will be asked to have all EOT safety evaluations performed as described in the protocol (see the Schedule of Assessments). If a patient withdraws from treatment during Cycle 1 due to any reason other than a DLT and does not meet the minimum requirements for inclusion in the MTD-determining population described in Section 5.1.1, that patient will be replaced. The level of patient's withdrawal will be documented (withdrawal from study treatment; withdrawal from study treatment and assessments but allowing survival follow-up; or full withdrawal from the study, with no survival follow-up permitted).

7.7 Pharmacokinetic Assessments

The plasma PK parameters (including $AUC_{(0-\infty)}$, $AUC_{(0-\tau)}$, C_{max} , t_{max} , and $T_{1/2}$) of AC699 following oral administration will be assessed by analysis of blood samples (See Appendix F).

During treatment, PK blood samples will be taken at approximately the following time points:

- Cycle 1 Day 1, and Day 15:
 - O Pre-dose; at 1, 2, and 4-hour post-dose (\pm 5 min); 6 and 8-hour post-dose (\pm 10 min); and 24 hours post-dose (\pm 1 hour)
- Cycle 2, 3, 4, and 6 Day 1: pre-dose only

CONFIDENTIAL

Study Drug: AC699 Sponsor/Development Innovations Study Numbers: AC699-001/BRE 401

Should a patient require a dose change, additional PK samples to ensure safety and efficacy parameters, may be required. These PK samples will be collected at the first cycle following the dosing change, at the same time points as Cycle 1 Day 1 and Cycle 1 Day 15. Subsequent predose PK samples may be requested at the next 3 cycles following the dosing change. Decisions as to whether or not these samples are to be collected will be determined in consultation with the Medical Monitor.

Additional unscheduled PK samples may be drawn during the study if it is felt that it may affect the safety of the patient. Similarly, if any PK time point is later deemed unnecessary per acquired clinical PK data, such time point(s) may be removed from the PK schedule.

7.8 Biomarker Assessments

7.8.1 Biomarker Tissue Samples

7.8.1.1 Optional Fresh Biopsies

Fresh tumor biopsies at baseline and on-treatment (within 28 days following the Cycle 2 Day 1 visit) are optional. All fresh biopsies will be processed according to the Laboratory Manual.

Evaluable baseline and on-treatment biopsy samples will be used to evaluate the amount of $ER\alpha$ degradation during treatment. If possible, sites should collect pre- and on-treatment biopsies from the same tumor lesion. Accessible lesions are defined as tumor lesions that can be biopsied without undue risk for the patient and that are amenable to repeat biopsies unless clinically contraindicated or the patient has withdrawn consent.

The physician will discuss the procedure with the patient and will confirm if they will be willing to undergo the biopsy procedure.

Instructions regarding sample collection, handling/processing and shipping are provided in the Laboratory Manual.

7.8.2 Biomarker Blood Samples

Blood samples will be collected for exploratory analysis of biomarkers to assess ctDNA and CTC levels. Blood samples for ctDNA will be collected pre-dose on Day 1 of Cycle 1 and Cycle 2, and at the EOT visit. CTC will be collected pre-dose on Day 1 of Cycle 1 and Cycle 2, and on Day 1 of all even numbered cycles thereafter, and at the EOT visit. Instructions regarding sample collection, handling/processing, and shipping are provided in the Laboratory Manual.

8. DRUG FORMULATION, AVAILABILITY, ADMINISTRATION, AND TOXICITY INFORMATION

8.1 AC699

Study Drug: AC699

Investigational Product	Dosage Form and Strength	Manufacturer
AC699	As described in the Pharmacy Manual	Accutar Biotechnology, Inc.

CONFIDENTIAL

Sponsor/Development Innovations Study Numbers: AC699-001/BRE 401

8.1.1 Labeling, Packaging, and Supply

AC699 will be supplied by Accutar Biotechnology, Inc. as described in the Pharmacy Manual.

At the start of each cycle, patients will be dispensed sufficient supplies until the next cycle. Study drug compliance will be assessed at each patient visit by review of the dosing diary. The research staff will count and document the amount of study drug taken and returned by the patient. The batch number of the study drug dispensed to the patient should be entered on the eCRF, if applicable.

The immediate packaging will contain a statement to conform with FDA Investigational New Drug (IND) requirements as follows: "Caution: New Drug - Limited by federal (or United States) law to investigational use."

All study drugs must be kept in a secure place under appropriate storage conditions. Storage conditions for AC699 are included on the investigational product label.

The Sponsor or its representative must be granted access on reasonable request to check drug storage, dispensing procedures, and accountability records.

8.1.2 Preparation and Administration of AC699

All patients entering this study will receive AC699 PO. The drug should be taken whole with liquid(s) and with food in the morning. The patient should avoid taking other medications at the same time as AC699. When possible, the patient should take other medications in the evening or separated by a minimum of 4 hours following AC699 dosing. The following will be recorded in the dosing diary: exact time of AC699 dosing during the study, and the time of dosing of concomitant medications in a Concomitant Medication Log during the first cycle from Cycle 1 Day 1 through Day 15. If having the patient delay taking other medications 4 hours following AC699 dosing is not feasible please discuss with the Medical Monitor and document.

• The time of day for administration of AC699 should be consistent. On PK collection visits, patients should be instructed to bring the study medication with them to the clinic and will take the dose after the pre-dose PK is taken. If the patient misses a dose of study drug, the patient should take the dose as soon as possible, but not less than 12 hours before the next dose is due. If the next dose is due in less than 12 hours, the patient should skip the missed dose and take the next dose as scheduled.

If vomiting occurs after taking the study treatment, the patient should be instructed not to retake the dose. Patients should take the next scheduled dose of AC699. If vomiting persists, the patient should contact the Investigator.

8.1.3 Precautions and Risks Associated with AC699

Precautions and risks are located in the IB.

8.2 Accountability for All Study Drugs

The Principal Investigator (or designee) is responsible for accountability of all used and unused study drug supplies at the site.

All study drug inventories must be made available for inspection by the Sponsor or its representative, e.g., Development Innovations, and regulatory agency inspectors upon request. Throughout the study and at its completion, Drug Accountability Record Form(s) will be

CONFIDENTIAL

Sponsor/Development Innovations Study Numbers: AC699-001/BRE 401

Final Protocol: 07 May 2024 Version 4.0

completed by the site and sent to the Development Innovations Regulatory Department. Study drug supplies must not be destroyed unless prior approval has been granted by the Sponsor or its representative. Please contact the Sponsor or its representative regarding disposal of any study drug.

9. RESPONSE EVALUATIONS AND MEASUREMENTS

Response and progression will be evaluated in this study using RECIST Version 1.1 (see Appendix B). Lesions are either measurable or non-measurable according to the criteria.

10. STATISTICAL CONSIDERATIONS

10.1 Statistical Design

This study is a Phase I, first-in-human, open-label dose-escalation study of AC699 given as a single agent. Pending the totality of data, including but not limited to safety and pharmacokinetics, selected dose levels may be expanded to approximately 20 patients (per dose level) to further support the evaluation of the Objectives set hereabove. Approximately 100 patients may be enrolled in this study.

Additional details on statistical design and evaluation of specific endpoint variables are provided in the Statistical Analysis Plan (SAP).

10.2 Sample Size Considerations

The actual number of dose levels to be explored in this study will depend on determination of the non-tolerable dose based on DLTs. The MTD will be defined based on DLTs. Other safety data, as well as PK profiles observed during the conduct of the study and any trends for anti-tumor activity will also be collected. Treatment cycles will occur consecutively as per the Schedule of Assessments. If one patient experiences a DLT at a given dose level, then that dose level will be expanded to 6 patients. Evaluation of a cohort of at least 3 patients completing 1 cycle of treatment (28 days) is required prior to proceeding to the next dose level. In addition, selected dose levels may be expanded to approximately 20 patients (per dose level).

The study will enroll approximately 100 patients, but the actual number will depend on the actual data.

10.3 Analysis Population

The following analysis populations will be used:

- Full Analysis Set (FAS)/ Safety Analysis Set (SAS) is defined as all patients who have received at least one dose of study treatment. Patients will be included in the cohort in which they have been actually treated.
- Efficacy Evaluable Set (EFF) is defined as all patients who have received any dose of study treatment and have at least one adequate post-baseline response assessment.
- PK Analysis Set (PAS) is defined as all patients who have received at least one dose of study treatment and have at least one sample collection of blood with a measurable concentration of study drug in plasma.

CONFIDENTIAL

Sponsor/Development Innovations Study Numbers: AC699-001/BRE 401

Final Protocol: 07 May 2024 Version 4.0

10.4 Data Analysis

Descriptive statistics, including mean, median, standard deviations and ranges for all continuous measures will be tabulated and reported. Percentages and frequencies for all categorical measures will also be presented. Time to events endpoints will be reported using Kaplan-Meier estimates, with 95% confidence intervals (CIs) for median time to event.

10.4.1 Demographics and Baseline Characteristics

Demographic and baseline disease characteristics will be summarized descriptively. Data to be tabulated will include demographic features such as age, sex, and race, as well as disease-specific characteristics.

The number and percentages of patients screened, randomized, treated, completed the treatment/study, and withdrawn from treatment/study for any reasons will be presented overall and also by dose level.

10.4.2 Efficacy Analysis

All efficacy analyses will be performed using the Efficacy Evaluable Analysis Set.

- Objective Response Rate (ORR), defined as the proportion of patients who have measurable disease at baseline with confirmed CR or PR (i.e., 2 CRs or PRs at least 4 weeks apart) according to the RECIST Version 1.1 criteria (see Appendix B).
- Clinical Benefit Rate (CBR), defined as the proportion of patients with CR, PR, or SD (where SD is ≥24 weeks) according to the RECIST Version 1.1 criteria.
- Duration of Response (DOR), defined as the time between first documentation of a response (CR or PR) and first evidence of PD according to RECIST v1.1 or death due to any cause.
- Disease Control Rate (DCR), defined as the proportion of patients with a best overall response of CR, PR, or SD (where SD is \geq 24 weeks).
- Progression-Free Survival (PFS), defined as the time from the first day of study drug administration (Day 1) until disease progression as defined by the RECIST Version 1.1 criteria, or death on study, whichever occurs first. Patients who are alive and free from disease progression will be censored at the date of last tumor assessment.

For ORR and CBR, estimates and the associated 95% CIs (based on the Clopper-Pearson method), at each dose level will be calculated. The absolute and relative difference in ORR and CBR between the two treatment groups will also be presented.

For PFS, Kaplan-Meier curves will be generated and the median time to event, and the associated 95% CIs will be provided. The hazard ratio and the 95% CIs for these endpoints between the two treatment groups will be calculated.

CONFIDENTIAL

Sponsor/Development Innovations Study Numbers: AC699-001/BRE 401

Final Protocol: 07 May 2024 Version 4.0

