5.1.2 Time-to-Event Variables

Time-to-event variables are defined as:

Time-to-Event (months) = (End Date - Start Date + 1) / 30.4375

 $DOR = (Earliest\ Date\ of\ Progression\ or\ Death-Date\ of\ First\ Documented\ CR\ of\ PR + 1)/30.4375.$

Start Dates

For all time to event variables other than DoR, the date of first dose of AC699 will be used as the start date.

The start date for DoR will be the date of first PR or CR, which has been subsequently confirmed.

End Dates

For DoR and PFS, the following rules will be used to derive the end dates for these endpoints:

- Events always take precedence to Censoring
- If multiple event dates are applicable, the earliest date will be used.
- If multiple censoring dates are applicable, the latest date will be used.

Table 2 shows data sources that can be used to determine end dates.

Table 2: Data Sources for End Dates

Date	Data Source	
Date of Death	Death CRF	
Date of Progression	Using RECIST 1.1 criteria, the earliest of the dates from the components that triggered the overall PD response from the Target Lesions, Non-target Lesions and New Lesions CRFs.	
Date of Last Evaluable Tumor Assessment	The latest data from the Target Lesions, Non-Target Lesions, and New Lesions CRFs reflecting the overall response, where the overall response is evaluable (i.e., not missing or NE), prior to further subsequent anticancer therapy if initiated.	
Date of Subsequent Anticancer Therapy	The earliest date is from the Subsequent Systemic Therapy, Subsequent Radiation, and Subsequent procedure CRFs.	

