5.1.3 Participant Follow-up

Participants are expected to be followed from the date of first dose of AC699 until the end of the study or death, whichever occurs first. Participants who discontinue the study treatment will continue to be followed up for disease progression (after the 30-day safety follow-up) through the end of the whole study as per the Protocol section 7.4.3: follow-up visits will be performed every 8 weeks (± 5 days) for the first year after treatment ends and then every 16 weeks (±5 days) thereafter until disease progression based on RECIST 1.1 or another withdrawal criterion is met:

- Start of a new anti-cancer therapy
- Lost to follow-up

Page 18 of 28

- Death
- Patient withdrawal
- End of the whole study

5.2 **Endpoints**

5.2.1 **Best Overall Response**

Best overall response (BOR) is defined as per RECIST 1.1 and will be calculated as the best response recorded from date of first dose of AC699 up until evidence of progression per RECIST 1.1.

The frequency and percentage of participants with each response will be summarized.

Confirmation of response is required (i.e., consecutive CRs, consecutive PRs or 1 CR and PR at least 4 weeks apart).

See Table 3 for scenarios of overall response.

Table 3: Best Overall Response with Confirmation of CR and PR Required

Overall Response			
Initial Subsequent		BEST Overall Response	
CR	CR	CR	
CR	PR	SD, PD, or PR*	
CR	SD	SD if minimum criteria for SD duration met, otherwise PD	
CR	PD	SD if minimum criteria for SD duration met, otherwise PD	
CR	Missing	SD if minimum criteria for SD duration met, otherwise NE	
PR	PR	PR	
PR	CR	PR	
PR	SD	SD	
PR	PD	SD if minimum criteria for SD duration met, otherwise PD	
PR	Missing	SD if minimum criteria for SD duration met, otherwise NE	

Abbreviations: CR = complete response, PR = partial response, SD = stable disease, PD = progressive disease, NE = not evaluable

When SD is believed to be the BOR, SD must have met the minimum interval of 7 weeks (8 weeks - 1 week for early assessments within window) since start of AC699. If it does not

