^{*}If a CR is truly met at first time point, then any disease seen at a subsequent time point, even disease meeting PR criteria relative to baseline, makes the disease PD at that point (since the disease must have reappeared after CR). Best response would depend on whether minimum duration of SD was met. However, sometimes 'CR' may be claimed when subsequent scans suggest small lesions were likely still present and in fact the patient had PR, not CR at the first time point. Under these circumstances, the original CR should be changed to PR and the best response is PR.

meet the minimum interval and there are no subsequent assessments indicating the participant had a PD, the BOR would be NE.

If a CR or PR cannot be confirmed, the BOR is dependent on the subsequent timepoint response. If the subsequent timepoint response is NE or there is no subsequent timepoint response, the BOR would be SD provided the minimum criteria for SD duration is met, otherwise NE. The unconfirmed responses (unconfirmed CR and unconfirmed PR) will be summarized as a sub-category of SD, and SD not meeting the minimum interval of 7 weeks (8 weeks – 1 week for early assessments within window) will be summarized as a subcategory of NE.

5.2.2 **Objective Tumor Response**

The following endpoints, along with their 95% CI, will be presented based on the objective tumor response:

- ORR = proportion of participants with a BOR of confirmed CR or PR.
- CBR = proportion of participants with a confirmed CR, or PR or a SD for ≥ 6 months according to the RECIST 1.1 criteria, where duration of SD is defined the date of last SD assessment the start date of study drug.
- DCR = proportion of patients with a best overall response of CR, PR, or SD (where SD is >= 6 months).

The denominator will be the number of participants in the EFF analysis set, and includes participants with a BOR of NE.

5.2.3 **Duration of Response**

Only participants with measurable disease whose BOR is CR or PR will be included in the analysis.

DoR (months) is defined as the time from first documentation of response (CR or PR, subsequently confirmed) to the first documentation of disease progression or death due to any cause. Participants who have neither progressed nor died will be censored.

Refer to **Table 4** for the event/censoring rules and dates to be used.

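### The 24-week stable-disease cut-off for CBR and DCR has no allowance for the ±5-day scan window, so an early but compliant week-24 scan that is the last SD assessment misses it; fix together with the 24-week versus 6-month conflict

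*Protocol*

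**What the plan says.** **Cut-off.** Protocol 10.4.2 defines CBR as the "proportion of patients with CR, PR, or SD (where SD is ≥24 weeks") and puts the same 24-week condition on SD in DCR. It does not say from which date to which date SD is measured.

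**Scan schedule.** Protocol 7.3.4: "Patients will be evaluated for response after 2 cycles of treatment" and "Response will be assessed every 2 cycles / 8 weeks (± 5 days) for the first year of treatment".

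**Duration rule.** Only the SAP has one. SAP 5.2.2 says that "duration of SD is defined the date of last SD assessment the start date of study drug". The operator seems to have been lost when the text was extracted; the natural reading is last SD assessment minus start date.

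**The SAP's cut-off.** SAP 5.2.2 pairs that rule with a different threshold, the "proportion of participants with a confirmed CR, or PR or a SD for ≥ 6 months according to the RECIST 1.1 criteria", and uses 6 months for DCR too. SAP section 8 records no change from the protocol.

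**Window allowances.** For SD as best overall response, SAP 5.2.1 says "SD must have met the minimum interval of 7 weeks" and explains this as 8 weeks less one week for early scans. The text under Table 4 in SAP 5.2.4 widens the two-missed-scans thresholds to 18 and 34 weeks for the same reason. SAP 5.2.2 makes no allowance, and SAP 3.4.4 rules out visit windowing.

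**The concern.** The third scheduled scan is due on the very day at which the Protocol's SD cut-off is reached, and the schedule lets it be done up to 5 days sooner. Take two patients with the same course, SD at week 24 and PD at week 32. If one is scanned on day 165 after first dose and the other on day 168, both are on schedule, but only the second counts toward CBR and DCR.

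The misclassification goes one way. An early week-24 scan can remove benefit; a late week-16 scan, at most 117 days after first dose, cannot create it. The SAP recognises this problem at the first SD assessment and in the missed-scan rule, so its absence here looks like an oversight. Protocol 10.4.2 plans CBR with exact intervals at each dose level, where one patient carries visible weight.

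**Working it through.** **1. The SAP's own allowances.**
- First SD scan: 8 weeks − 5 days = 56 − 5 = 51 days = 7.29 weeks. Rounded down, this is the stated 7 weeks.
- Two missed scans, year 1: (2 × 56 + 10)/7 = 17.4 weeks. Rounded up, this is the stated 18.
- Two missed scans, later: (2 × 112 + 10)/7 = 33.4 weeks. Rounded up, this is the stated 34.

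Each threshold makes room for the ±5 days.

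**2. Compliant scan dates against each cut-off.** Inputs: 8-week interval and ±5 days (Protocol 7.3.4); 24 weeks = 24 × 7 = 168 days (Protocol 10.4.2); 6 months = 6 × 30.4375 = 182.6 days. The last uses the SAP 5.1.2 convention "Time-to-Event (months) = (End Date - Start Date + 1) / 30.4375"; applying it to SD duration is an assumption. Dates are counted from first dose.

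| Last SD scan | Compliant days | Fail 168 days | Fail 182.6 days | Fail 163 or 161 days |
|---|---|---|---|---|
| Week 16 | 107–117 | 11 of 11 | 11 of 11 | 11 of 11 |
| Week 24 | 163–173 | 5 of 11 | 11 of 11 | 0 of 11 |
| Week 32 | 219–229 | 0 of 11 | 0 of 11 | 0 of 11 |

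The five failing week-24 days are 163 to 167. If one day is added, as in the SAP 5.1.2 formula, durations become 164 to 174 and 4 of 11 fail the 168-day cut-off.

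**3. Effect per dose level.** With 20 evaluable patients (Protocol 10.2 gives approximately 20 per expanded level), one patient is 1/20 = 5 points. For example, 8/20 = 40% (Clopper-Pearson 95% CI 19.1 to 63.9) becomes 7/20 = 35% (15.4 to 59.2).

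**4. Expected loss, on assumed inputs.** The documents give no progression rate, response rate or scan-timing pattern. Assume exponential progression with median 4 to 10 months, ORR 10 to 30%, response independent of progression, and no other drop-out. The share of patients with week 24 as last SD scan is then (1 − ORR) × [S(168) − S(224)], with S(t) = 0.5^(t/median in days).
- Median 4 months (121.75 days), ORR 10%: 0.9 × (0.3843 − 0.2794) = 9.4%.
- Median 10 months (304.375 days), ORR 30%: 0.7 × (0.6821 − 0.6004) = 5.7%.

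With scan dates uniform over the window, multiply by 5/11: 5.7% gives 2.6 points of CBR and 9.4% gives 4.3. With one day added, multiply by 4/11: 2.1 and 3.4 points.

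If the share is simply taken as 5% to 20%, the 5/11 factor gives 2.3 to 9.1 points.

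**The case against.** The strongest objection is that neither document, read alone, produces this failure. The Protocol supplies 24 weeks but no end date for SD; if SD ran to progression, SD on day 163 with PD at week 32 would pass. The SAP supplies the end date but pairs it with 6 months, where every compliant week-24 scan fails and every compliant week-32 scan passes, so ±5 days changes nothing. This stands. The window matters only if the conflict is settled at 24 weeks and the last-SD-assessment rule is kept. That is nevertheless a likely outcome: the SAP still describes about 60 patients and 15 per expanded level against 100 and 20 in Protocol version 4.0, so it needs updating, and bringing only its cut-off into line would expose the gap.

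A reader might infer that any early week-24 scan costs the patient clinical benefit. It does not. The scan must be the last SD assessment; confirmed CR or PR, or SD again at week 32, removes the problem.

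The 163-to-173-day range assumes counting from first dose. Protocol 7.4.3 says so explicitly only for extended follow-up. On treatment, scans are tied to cycles as well as weeks, and section 6 allows dose delays. If delays shift the scans, dates move later and fewer fail.

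Finally, a strict nominal cut-off is a legitimate definition, the first-scan rule concerns best overall response rather than SD duration, and the consequence is modest. CBR is secondary, no hypothesis is tested, and efficacy data are listed, so borderline patients remain visible. All of this limits the weight of the point without explaining why early scans are allowed for elsewhere and not here.

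**Conclusion.** The gap is real but conditional. With the Protocol's 24-week cut-off and the SAP's duration rule, a patient whose last SD assessment is a compliant week-24 scan done 1 to 5 days early is counted as a failure for CBR and DCR. The count of failing days depends on the day convention, which SAP 5.2.2 leaves unclear.

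The documents do not support reading this as a bias of known size. The 2-to-4-point figure is illustrative, resting on the assumed progression, response and uniform scan timing. Nothing shows that sites habitually scan early. What can be said firmly is the direction (CBR and DCR can only be understated) and the unit, 5 points per patient at 20 per level.

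The 24-week versus 6-month conflict matters more, and the two cannot sensibly be settled apart. The allowance is worth adding because it is cheap and follows the SAP's own practice. In an open-label trial it should be fixed before the analysis, so that borderline patients are not classified with results in view.

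**What to change.** Make one edit to SAP 5.2.2, for both CBR and DCR:

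1. Replace 6 months with the Protocol's 24 weeks, and align the endpoint table in SAP 1.2.
2. State how SD duration is counted: start date, end date, and whether one day is added.
3. Count SD as lasting at least 24 weeks when the last SD assessment is at least 163 days after first dose (168 − 5, the scan window). Alternatively use at least 23 weeks (161 days), matching the one-week allowance in SAP 5.2.1.
4. Cross-refer from Protocol 10.4.2.

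Either threshold accepts all 11 compliant week-24 days and no compliant week-16 scan. The cost beyond the cut-off correction is about one sentence. The downside is that, for a few patients, nominal SD will be up to 5 days short of 24 weeks (up to 7 under the 23-week version).
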